3.4 Adherence and Protocol Deviations

3.4.1 Adherence to Allocated Treatment

Adherence to the allocated study treatment will be assessed for all participants who receive at least one dose of investigational medicinal product (IMP). Adherence is defined as the extent to which participants take the study medication according to the prescribed dosing regimen.

Compliance will be assessed using capsule counts and subject diaries and will be calculated as:

$$\% \text{ Compliance} = \left(\frac{\text{Number of capsules taken}}{\text{Number of capsules prescribed}} \right) \times 100$$

The number of capsules prescribed will be calculated based on the duration of treatment (date of last dose – date of first dose + 1) multiplied by the number of capsules prescribed per day according to the assigned dose level.

Compliance will be summarized by treatment group and overall. Participants will be classified as compliant if their calculated compliance is within 80–120% of the prescribed dosing, in accordance with the protocol definition.

The following summaries will be presented:

- Mean, median, and range of percentage compliance
- Number and percentage of participants classified as compliant
- Number and percentage of participants with compliance <80% or >120%

Compliance summaries will be descriptive only and no formal statistical comparisons will be performed.

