To evaluate compliance, the study will measure the extent to which participants take the study medication according to the protocol. Compliance will be assessed using the subject diary and the registration of returned capsules.

Exploratory Objectives:

To evaluate changes in specific biomarkers of Alzheimer's Disease (AD) in cerebrospinal fluid (CSF): A β 1-40, A β 1-42, Tau, and p-tau, and in blood plasma: p-tau217 and NfL.

To assess phenserine's potential short-term effects on specific cognitive tests using the FLAME Memory Composite and other cognitive sub-tests.

To evaluate changes in overall cognitive function using the Montreal Cognitive Assessment (MoCA):

Primary Endpoint:

Changes in exosome biomarkers of pre-programmed cell death, synaptic integrity and function, neuroinflammation, and AD-related protein trafficking in participants treated with phenserine versus those treated with donepezil. Although patients and site staff will be unblinded to the treatment modality administered, they will be blinded to the results of the biomarker evaluations until the study is completed.

Key Secondary Endpoints:

Safety and tolerability of phenserine compared to donepezil in participants with early or mild AD based on the frequencies of reported or observed adverse events (AEs) and serious adverse events (SAE), vital signs, clinical laboratory evaluations, ECGs, and modified CSSRS scores.

Other Secondary Endpoints:

Pharmacokinetic parameters will be assessed at steady state for determination of dose-response relationships for phenserine and donepezil.

Evaluate the proportion of participants in the phenserine arm who achieve the target AChE inhibition of approximately 45%, stratified by dose regime and assess the time required to reach the target AChE inhibition of ~45% and the duration participants maintain this inhibition during the treatment period. Blood samples will be analyzed for Acetylcholinesterase (AChE) activity using a modified Micro-Ellman method (22) normalized to recombinant AChE enzyme activity (refer to Appendix 10).

Compliance will be recorded, based on drug count and subject diary, including the proportion of participants complying with the treatment schedule. Compliance is defined as drug intake within 80-120% of the scheduled dosing.

Exploratory Endpoints:

Assess changes in Alzheimer's Disease (AD) biomarkers in cerebrospinal fluid (CSF): A β 1-40, A β 1-42, Tau, and p-tau, and in blood plasma: p-tau217 and NfL.

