2.3 Exploratory Objectives

- Changes in CSF and plasma AD biomarkers
- Short-term cognitive effects using FLAME and MoCA

Endpoints are defined exactly as per Protocol Section 3 and Table 2

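### The SAP compliance denominator ends at the last dose, so a participant who stops early without instruction can be classed as compliant with the 8-week schedule

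*SAP*

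**What the plan says.** **Protocol.** Compliance is listed in Section 3 under Other Secondary Endpoints and again in Table 2. It is to be reported from drug counts and the diary, "including the proportion of participants complying with the treatment schedule". The definition follows: "Compliance is defined as drug intake within 80-120% of the scheduled dosing". Sections 3.2.2 and 6.5 repeat the 80-120% window against scheduled dosing. The planned treatment period is 8 weeks.

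**SAP.** Section 2.3 states: "Endpoints are defined exactly as per Protocol Section 3 and Table 2". Section 3.4.1 covers "all participants who receive at least one dose of investigational medicinal product (IMP"), so early stoppers are included. Percentage compliance is capsules taken divided by capsules prescribed. The prescribed number is "based on the duration of treatment (date of last dose – date of first dose + 1"). Those days are then scaled by the daily capsule count for the dose the participant was on. A participant counts as compliant if "compliance is within 80–120% of the prescribed dosing, in accordance with the protocol definition".

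SAP 8.4 adds only the percentage of prescribed doses taken and the proportion inside the window. SAP 11 lists no change to the compliance definition.

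**The concern.** The two documents use different end points for the denominator. Scheduled dosing in an 8-week regimen naturally runs to the planned end of treatment unless the site changes the plan. The SAP denominator runs only to the last dose. The two agree for anyone who completes treatment. They part when a participant stops without instruction while still scheduled to take drug, because the remaining scheduled doses are then never counted as missed.

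Such a participant remains in view. Protocol Section 7 keeps participants who stop treatment under assessment to Week 8 unless consent is withdrawn, and the SAP mITT definition needs only one dose and one post-baseline exosome sample. The report could therefore call compliant someone who took a fraction of the planned course. The trial is meant to inform a Phase 2 dose range, and readers will use the compliant proportion to judge whether the regimen was taken as planned.

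**Working it through.** The plan states no expected compliance rate, so there is no figure to reproduce. The check applies the SAP formula and the full-schedule denominator to the same intake.

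**Inputs** (Protocol 6.6 and Table 3), assuming 56 dosing days and tablets counted as capsules are:
- Phenserine, fully escalated: 14 × 2 + 14 × 2 + 28 × 3 = 28 + 28 + 84 = 140 capsules.
- Phenserine kept at twice daily: 56 × 2 = 112 capsules.
- Donepezil: 56 × 1 = 56 tablets.

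**Formulas.**
- SAP: taken ÷ units prescribed from first to last dose.
- Schedule: taken ÷ units prescribed over 8 weeks.

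A full completer scores 140/140 or 56/56, which is 100% either way.

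**Every dose taken, then an undirected stop:**

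| Stop after | Phenserine, SAP | Phenserine, schedule | Donepezil, SAP | Donepezil, schedule |
|---|---|---|---|---|
| 14 days | 28/28 = 100% | 28/140 = 20% | 14/14 = 100% | 14/56 = 25% |
| 28 days | 56/56 = 100% | 56/140 = 40% | 28/28 = 100% | 28/56 = 50% |
| 42 days | 98/98 = 100% | 98/140 = 70% | 42/42 = 100% | 42/56 = 75% |

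**Imperfect intake before the stop.** Taking 45 of 56 phenserine capsules and stopping after 28 days gives 45/56 = 80.4% under the SAP (compliant) and 45/140 = 32.1% of schedule. The 11 doses missed before the last dose are counted. The 84 scheduled afterwards are not.

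**Where the class changes on the full schedule (otherwise perfect intake):**
- Phenserine, fully escalated: 46 days gives (56 + 18 × 3)/140 = 110/140 = 78.6%; 47 days gives 113/140 = 80.7%. Stops at 46 or fewer dosing days are reclassified.
- Phenserine at twice daily: 44 days gives 88/112 = 78.6%; 45 days gives 90/112 = 80.4%. The limit is 44 days.
- Donepezil: 44/56 = 78.6%; 45/56 = 80.4%. The limit is 44 days.

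**If the site records a stop instruction at the next visit** and the denominator ends there (phenserine):
- Stop after day 14, recorded at Week 4: 28/56 = 50%, below the window.
- Stop after day 40, recorded at Week 6: (56 + 12 × 3)/(56 + 14 × 3) = 92/98 = 94%, still compliant.

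**Effect of one participant on the arm proportion.** 1/12 = 8.3 points on phenserine and 1/4 = 25 points on donepezil. For illustration, if 3 of 12 on phenserine stopped undirected by day 28, no stop instruction was recorded and the rest were perfect, the SAP would report 12/12 (100%) and the schedule would give 9/12 (75%).

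**The case against.** The best defence is that the SAP separates persistence from dose-taking. SAP 3.3 tabulates, by arm, participants who did not complete or withdrew from the intervention, with reasons. SAP 8.1 reports discontinuations. On that view 3.4.1 measures only how well drug was taken while it was being taken, and the protocol never says that scheduled dosing continues past a discontinuation. This stands for site-directed discontinuation, where an on-treatment denominator is defensible. It does not cover a participant who is still scheduled to dose, because the other tables leave the compliance percentage and class unchanged.

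The phrase date of last dose might also be meant as the planned last dose. The SAP does not say so, and the ordinary meaning is the last dose taken. If the planned date was intended, the sentence still needs clarifying.

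Three stronger readings are tempting, and the documents do not support them:
- *A reader might infer that compliance will look near-complete whatever happens.* Gaps before the last dose remain in the denominator. If a stop is found at a visit and dosing resumes, the last-dose date moves later and the gap is counted.
- *A reader might infer that off-drug time is hidden behind the biomarker and AChE results.* Table 1 schedules AChE and PK samples at Weeks 2, 4, 6 and 8. Returned drug is counted at those visits, stop dates are recorded (Protocol 6.5), and compliance is not a term in the exosome model (SAP 7.2).
- *A reader might infer that early self-stopping is the commonest serious form of non-adherence here.* Nothing in the documents says so. Protocol 2.3.1 reports that nausea and vomiting did not contribute to dropouts in the earlier 12-week trial.

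**Conclusion.** The concern holds for undirected stopping. As written, SAP 3.4.1 does not measure the protocol's compliance endpoint in that case, although it claims to follow the protocol definition.

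The size depends on when the site documents the stop. With no recorded instruction, the SAP's 100% corresponds to the 20-70% (phenserine) or 25-75% (donepezil) of schedule tabulated above. With an instruction recorded at the next visit the gap is smaller, and a late stop may not change class at all. These figures rest on 56 dosing days, the dose paths stated and otherwise complete intake. The documents give no rate of undirected stopping, so the number of participants affected cannot be predicted.

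The consequence is limited. Compliance is a descriptive secondary endpoint, no analysis population is defined by it and no test uses it. It should be corrected because the change is small and, with 12 and 4 participants, a single misclassification is visible in the reported proportion.

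**What to change.** Amend SAP 3.4.1 before database lock, through the SAP amendment route in SAP 1.1:

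1. Run the denominator from the first dose to the earlier of the scheduled end of treatment (Week 8 visit) or the documented date of site-directed discontinuation.
2. Sum units prescribed per day over each site-directed dose period, so that directed reductions or non-escalation are not counted as missed doses.
3. Keep the current first-to-last-dose percentage as a supplementary column, labelled as intake while taking drug.
4. State that tablets are counted in the same way as capsules.

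**Cost.** A short rewording and one extra table column. Protocol 6.5 already records quantities, start and stop dates, delays and reductions, and Protocol 7.2 requires the reason for discontinuation. It does not explicitly list the date of a site instruction to stop, so the data manager should confirm that this can be told apart from the date of last intake. The reported compliance rate may be lower.

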6.5. Study Intervention Compliance

When participants are dosed at the site, they will receive study intervention directly from the investigator or designee, under medical supervision. The date and time of each dose administered in the clinic will be recorded in the source documents. The dose of study intervention and study participant identification will be confirmed at the time of dosing by a member of the study site staff other than the person administering the study intervention.

When participants self-administer study intervention at home, compliance with study intervention will be assessed at each visit, and a subject diary will be completed. Compliance will be assessed by returned capsules/tablets, the subject diary, and during the site visits and documented in the source documents and relevant form. Deviation(s) from the prescribed dosage

regimen should be recorded. Compliance is deemed acceptable if within 80-120% of the scheduled dosing. A record of the quantity of dispensed study intervention to and administered by each participant must be maintained and reconciled with study intervention and compliance records. Intervention start and stop dates, including dates for intervention delays and/or dose reductions will also be recorded.

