- Repeat laboratory or clinical assessments (e.g., liver enzymes, eGFR, ECGs, or GI evaluations) will be conducted weekly or bi-weekly, depending on the severity of the abnormality, until resolution or stabilization.
- Comprehensive clinical evaluations, including symptom assessments, will be performed as needed.

3. Continuation of the study intervention

- Continuation of the study intervention of the study intervention will be considered only if the abnormality resolves or improves to a clinically acceptable level, as determined by the investigator and sponsor.

4. Participant communication: Participants will be informed of the findings, any changes to their treatment plan, and the rationale for either resuming or discontinuing the study intervention.

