9.17. Adverse Events (AEs) Serious Adverse Events (SAEs), and Other Safety Reporting

The definitions of adverse events (AEs) and serious adverse events (SAEs) can be found in Appendix 3.

The investigator and any qualified designees are responsible for detecting, documenting, and recording events that meet the definition of an AE or SAE and remain responsible for following up all AEs considered related to the study intervention or study procedures, or that caused the participant to discontinue the study intervention (see Section 7). This includes events reported by the participant (or, when appropriate, by a caregiver, surrogate, or the participant's legally authorized representative). Adverse events will be discussed with the local study doctor, and as needed discussed with the medical monitor. Based on the severity considering the safety of the participants, a decision will be made regarding dose reduction, pausing the study drug, or withdrawing the participant from the study.

The method of recording, evaluating, and assessing causality of AEs and SAEs and the procedures for completing and transmitting SAE reports are provided in Appendix 3.

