3.4.2 Protocol Deviations

A protocol deviation is defined as any departure from the approved protocol, including but not limited to deviations related to eligibility criteria, study treatment administration, study assessments, or visit scheduling.

Protocol deviations will be prospectively classified as major or minor prior to database lock and prior to unblinding of biomarker results.

Major Protocol Deviations

Major protocol deviations are defined as deviations that may affect participant safety, the scientific integrity of the study, or the interpretability of the primary endpoint.

Predefined major protocol deviations include:

- Failure to meet inclusion or exclusion criteria with enrolment into the study
- Receipt of incorrect study treatment or dose not consistent with protocol-defined escalation rules
- Discontinuation of study treatment prior to completion of the dose-escalation phase without post-baseline biomarker data
- Use of prohibited concomitant medication with potential impact on safety or pharmacodynamic outcomes
- Missing all post-baseline exosome biomarker assessments

Participants with major protocol deviations may be excluded from specific analysis populations as defined in Section 4.

Minor Protocol Deviations

Minor protocol deviations include deviations that are not expected to materially affect safety or interpretation of study outcomes, such as:

- Study visits conducted outside the protocol-defined visit window
- Isolated missed or delayed assessments
- Administrative or documentation errors

Summary of Protocol Deviations

Protocol deviations will be summarized descriptively by treatment group and overall. The following summaries will be provided:

- Number and percentage of participants with at least one protocol deviation
- Number and percentage of participants with at least one major protocol deviation
- Number and percentage of participants with at least one minor protocol deviation

- Listing of protocol deviations by category and type

Percentages will be calculated using the randomized population as the denominator. No formal statistical testing will be undertaken.

4 Analysis Populations

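### The SAP 3.4.1 compliance formula has no term for investigator-directed pauses, so a pause followed by resumption is scored as missed doses

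*SAP*

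**What the plan says.** Compliance is a named secondary endpoint. The objective in protocol section 3 is that "the study will measure the extent to which participants take the study medication according to the protocol"; the endpoint in the same section is intake between 80% and 120% of what was scheduled.

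SAP 3.4.1 divides capsules taken by capsules prescribed. It defines the latter as "duration of treatment (date of last dose – date of first dose + 1) multiplied by the number of capsules prescribed per day", at the assigned dose level. It then states: "Participants will be classified as compliant if their calculated compliance is within 80–120% of the prescribed dosing". Mean, median and range of compliance, the number compliant, and the number outside the window are all reported by arm.

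The protocol provides for interruptions:

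- Section 9.17, on adverse events, says that "a decision will be made regarding dose reduction, pausing the study drug, or withdrawing the participant from the study".
- Section 8 (Required Actions and Follow-Up) has participants told "the rationale for either resuming or discontinuing the study intervention". Its subsection 8.1.2 bars restart only for those who have met a stopping criterion.
- Section 6.5 requires that "Intervention start and stop dates, including dates for intervention delays and/or dose reductions will also be recorded".

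SAP 8.1 lists dose reductions and discontinuations by arm, but not interruptions.

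**The concern.** The elapsed-days denominator treats every day from first to last dose as a day on which capsules were due. If the study doctor pauses the drug and later restarts it, the paused days stay in the denominator and add nothing to the numerator. The participant has done what they were told, which is what the objective sets out to measure, yet the score records a shortfall.

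The stake is how one secondary endpoint is read. If one drug leads to more or longer pauses, its arm shows lower compliance for a reason that belongs to tolerability. The same pause also costs more in one arm than in the other, because phenserine at its top level accounts for a larger share of the course per day than donepezil does. With 12 and 4 participants, one reclassification is visible in the table. No planned SAP summary shows the pauses themselves, so a reader of the compliance table could not tell directed pauses from missed doses.

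**Working it through.** The documents give no compliance figure to reproduce, so the SAP 3.4.1 formula is applied directly.

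**Inputs**

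- Phenserine schedule (protocol 6.6 and Table 3): two capsules a day in Weeks 1–2, two a day in Weeks 3–4, three a day in Weeks 5–8.
- Donepezil: one tablet a day throughout (protocol Table 3), counted as the formula counts capsules.
- Window: 80–120% (SAP 3.4.1).
- Arm sizes: 12 and 4 (SAP section 3).
- Assumptions: 56 dosing days, titration on schedule, one pause followed by restart at the same level, and no other missed dose.

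**Capsules prescribed over a full course**

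- Phenserine: 14×2 + 14×2 + 28×3 = 140.
- Donepezil: 56×1 = 56.

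**Score after a directed pause of d days, with c capsules a day in the paused period**

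Compliance = (total − c×d) / total. It falls below 80% when c×d exceeds 20% of the total.

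| Situation | Longest pause still compliant | Shortest pause classed below 80% |
|---|---|---|
| Phenserine, 3 a day (Weeks 5–8) | 9 days: 113/140 = 80.7% | 10 days: 110/140 = 78.6% |
| Phenserine, 2 a day (Weeks 1–4) | 14 days: 112/140 = 80.0% | 15 days: 110/140 = 78.6% |
| Donepezil, 1 a day | 11 days: 45/56 = 80.4% | 12 days: 44/56 = 78.6% |

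A 10-day pause on donepezil gives 46/56 = 82.1%. The same 10 days therefore fail a phenserine participant at the top level and pass a donepezil participant.

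**Shorter course.** If phenserine treatment lasts only 28 days at two a day (56 capsules), a 6-day pause is enough: (56 − 12)/56 = 44/56 = 78.6%. Five days gives 46/56 = 82.1%.

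**Effect on the arm summary.** One reclassified participant moves the compliant proportion by 1/12 = 8.3 points or 1/4 = 25 points.

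**Permanent stops.** The denominator ends at the last dose. A phenserine participant who stops for good on day 35 has taken 28×2 + 7×3 = 77 capsules, against 77 prescribed: 100%. Only a pause that is followed by resumption lowers the score.

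**Which rate applies.** The formula is written as one product, although the phenserine rate changes during the course. At a single rate, a participant who took every capsule would score 140/(56×3) = 140/168 = 83.3%, or 140/(56×2) = 140/112 = 125%, which is outside the window. The formula must be meant to follow the dose level over time, but this is left to be inferred.

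**With directed-pause days set to zero.** Numerator and denominator fall together, and a participant who followed every instruction scores 100% whatever the length of the pause. As written, a 14-day pause at three a day scores (140 − 42)/140 = 98/140 = 70.0%.

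**The case against.** The best defence is that the formula can be read kindly. Adherence is defined against the prescribed regimen, and on a day when the doctor has stopped the drug nothing is prescribed, so that day contributes zero. This reading is sensible, but the SAP does not state it. What the SAP states is a span of calendar days multiplied by a daily rate set by dose level, and a pause is not a dose level. Two programmers could follow the text and report different results.

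A second defence is that the protocol endpoint refers to scheduled dosing, so the SAP does not depart from it. That is fair as to the endpoint. But the endpoint does not say whether a paused day is a scheduled one, and the objective it serves is adherence to the protocol.

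A third is that long pauses may be rare. Intolerance is handled mainly by returning to the previous dose level or by discontinuation; pausing is named in one clause of 9.17. Restart at a lower level also changes the arithmetic. Take 28 days at two a day, 7 days at three, a 10-day pause, then 11 days at two: capsules taken are 56 + 21 + 22 = 99. If pause days count at two a day, the score is 99/119 = 83.2%, compliant; at three a day it is 99/129 = 76.7%, non-compliant. This objection stands as to frequency, which the documents do not give. It also shows that the class can turn on a rate that the SAP does not specify.

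Finally, compliance is descriptive and defines no analysis set in SAP section 4. That stands, and it limits the consequence.

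**Conclusion.** The point holds for the compliance calculation. Under the formula as written, a directed pause followed by resumption counts as missed doses. It reclassifies a fully adherent participant at 10 days (three capsules a day), 15 days (two a day) or 12 days (donepezil), given a 56-day course and restart at the same level. The shifts of 8.3 and 25 points are per case; the number of cases is unknown. The primary biomarker estimate is not affected.

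A reader might infer three stronger things that the documents do not support:

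- *That protocol-ordered early stops are in general booked as major deviations.* SAP 3.4.2 lists "Discontinuation of study treatment prior to completion of the dose-escalation phase without post-baseline biomarker data", so a stop with any post-baseline biomarker data is not caught by that item. Protocol section 7 plans endpoint assessments at drop-out and at Week 8 unless consent is withdrawn. A participant with no post-baseline exosome sample is already outside the mITT population (SAP 4.3). What remains is narrow: neither that item nor the one on missing all post-baseline exosome assessments says that a stop required by protocol 7.1 is itself adherence to the protocol.
- *That safety stops lower compliance.* They do not, because the denominator ends at the last dose and restart after a stopping criterion is barred.
- *That intolerance is reported only as poor conduct.* SAP 8.1 reports adverse events, dose reductions and discontinuations by arm, SAP 3.3 reports reasons for withdrawal, and protocol 3.2.2 records the action taken for each adverse event. Only a summary of pauses is missing.

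**What to change.** In SAP 3.4.1, define capsules (or tablets) prescribed as the sum, over each day from first to last dose, of the number instructed for that day, with zero on days of a documented investigator-directed pause. This also settles which rate applies when the dose level changes. Pauses that the participant starts without instruction should stay in the denominator.

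In SAP 8.1, add interruptions to the dose reductions and discontinuations: number of participants, days and reason, by arm. A pause removed from the compliance score then remains visible as tolerability information.

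Optionally, SAP 3.4.2 could note that a stop required by protocol 7.1 is not itself a deviation, while failure to take the required drop-out samples still is. Exempting such participants from the missing-sample item altogether would hide missed sampling and is not advised.

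The cost is a short SAP amendment before database lock and a small change to the compliance program. Protocol 6.5 already has the dates recorded. The one condition is that source documents show who directed each pause, so that missed doses cannot be relabelled as pauses afterwards.
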